2.1.2.2 Visit windows for Safety Follow-up

For patients who prematurely discontinues treatment or do not enter the umbrella study after EOS, Safety Follow-up period should be entered. Visit windows are also defined.

The visit windows are defined in [Table 2-9](#), where the start day, target day, and end day are relative to EOS visit.

Table 2-9 Visit windows for Safety Follow-up period

Visit-window	Start day	Target day	End day
Week 12 post EOS	2	84	126
Week 24 post EOS	127	168	210
Week 36 post EOS	211	252	294
Week x post EOS*	$x * 7 - 42 + 1$	$x * 7$	$x * 7 + 42$

*if study goes beyond Week 36, every 12 weeks the same assessments on Week 36 will be performed. X will be a multiple of 12 weeks from Week 48 and beyond.

All days are relative to EOS visit. These visit windows will be applied only to assessments after the last date of study drug.

2.1.2.3 Multiple assessments within visit windows

It is possible that multiple assessments of a patient fall into the same visit-window (e.g. due to unscheduled visits). All results (scheduled and unscheduled) will be displayed in listings, but only one value (observed or derived) will be selected for summary statistics by visit-window.

For quantitative variables, the assessment closest to the target day will be selected. If more than one assessment is at the same distance to the target day, the later one will be selected. For tables displaying the worst case scenario, such as shift tables or notable abnormalities, all assessments within a visit window will be used to identify the worst (e.g. the maximum or the minimum depending on parameter).

For qualitative variables, the worst record is selected; it is noted that in the relevant data subsection, worst case is always well defined.

2.1.3 Nominal visits for ECG analysis

By-visit summary of ECG measurement uses nominal visits.

For Cut-off 2 and final analysis, analysis visits will be based on the treatment course of patients in the study.

- For a patient having ofatumumab treatment across Core and Extension parts, assessments at study visits Week 24 and 48 will be included in the summary of corresponding visits.
- For a patient switching the treatment from placebo to ofatumumab at Week 24, assessments from Week 48 visit will be included *in the summary of Week 24 visit*

2.1.4 Treatment group for Cut-off 2 and final analysis

For analysis based on Extension FAS, the following treatment groups will be displayed:

- OMB 20mg: This will include patients randomized to ofatumumab treatment group and having at least one dose of ofatumumab in Extension part.
- Placebo – OMB 20mg: This will include patients randomized to placebo treatment group, and having at least one dose of ofatumumab in Extension part.

For safety analysis based on Extension SAF, the following treatment groups will be displayed:

- OMB 20mg: This will include patients treated with ofatumumab during Core part and having at least one dose of ofatumumab in Extension part.
- Placebo – OMB 20mg: This will include patients treated with placebo during Core part, and having at least one dose of ofatumumab in Extension part. For these patients, analysis will include only assessments on or after treatment at Week 24, and Safety FU period if necessary.

2.2 Analysis sets

Full analysis set (FAS): The FAS comprises all randomized subjects with assigned treatments. Subjects will be analyzed according to the randomized treatment assignment following the intention-to-treat (ITT) principle, even if they actually received no or a different treatment.

The FAS will be used for the summary of demography and baseline characteristics and all efficacy analyses.

Extension FAS (EFAS): The EFAS will include all FAS subjects who received at least one dose of ofatumumab during Extension part. Analyses on EFAS will include *all* available efficacy assessments of the Core and Extension parts.

Per-protocol set (PPS): The PPS is a subset of FAS, consists of all randomized subjects who take at least one dose of study medication and have no major protocol deviations that could confound the interpretation of analyses conducted on the FAS. Major protocol deviations will be determined according to the pre-defined protocol deviation criteria before treatment unblinding (e.g. non-compliance for a large proportion of the time in study). For analyses performed on the PPS, only on-treatment assessments will be used.

The PPS will primarily be used for the supportive analyses of the primary efficacy variable.

Safety set (SAF): The SAF set includes all subjects who received at least one dose of study medication. Subjects will be analyzed according to the actual treatment received. The Safety Set will be used for all safety analyses for Cut-off 1 analysis.

Extension Safety set (ESAF): The ESAF set includes all subjects who received at least one dose of ofatumumab during Extension part. Subjects will be analyzed according to the actual treatment received. The Extension Safety Set will be used for all Cut-off 2 and final safety analyses. Analyses on ESAF will include safety assessments *only under ofatumumab treatment during the Core and Extension parts*.

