3.4 Rationale for choice of comparator

The primary goal of this study is to demonstrate the efficacy of ofatumumab 20 mg sc every 4 weeks on the inflammatory MRI lesions, by distinguishing ofatumumab from an appropriate control agent. The choice of placebo as a control agent is important to obtain information concerning the specific versus non-specific effects of the active treatment and provides the best way of evaluating the efficacy and of assessing the true safety and tolerability profile of ofatumumab.

The placebo-controlled study design allows the scientific and regulatory objectives of the study to be met with a smaller sample size than if an active comparator would be used, thus reducing the necessary number of patients especially from Japan and maintaining feasibility.

Currently, despite the availability of treatment for relapsing MS, the selection of placebo as a control agent in this study can be accepted by the following:

- Patients who randomized to placebo in a 24-week Double-blind treatment period (Core part) and complete its period will have the opportunity to receive ofatumumab 20 mg sc every 4 weeks in the Extension part.
- Patients should be informed by the investigators about locally available approved MS therapies for treating their MS and about the probability to receive the placebo based on randomization in a 2:1 ratio to either ofatumumab or placebo in this study. Patients need to consent in writing.
- A standard short course of corticosteroids may be used to treat MS relapses based on investigator's judgment. Patients who have MS relapses during this study will be informed again about the current available treatments for patients with relapsing MS. If the patients agree to stay in this study, they will be asked to sign the informed consent form to document their decision.
- Patients can select to discontinue study treatment and consider to start treatment with an approved MS therapy. The duration of the washout period after last dose of study drug will depend on the type of therapy to be initiated and the patient's clinical condition (see [Section 5.6.2](#)).

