9.7 Analysis of the Extension part

Analyses will include the combined data of the Core and Extension parts.

The extension FAS will include all available assessments of the Core and Extension parts. The main between-group comparisons of the efficacy variables will be based on the original randomization at the start of the Core part. The comparison will be between patients who were randomized to ofatumumab, and those who were initially randomized to placebo and received ofatumumab delayed, i.e. at the start of the Extension. Efficacy analyses will use similar models as described for the Core part of the study.

Extended safety and tolerability will be described by safety parameter summaries covering the whole period of continuous treatment with ofatumumab, i.e. by combining double-blind and open-label ofatumumab treatment. Placebo data will be excluded in this analysis. Details will be provided in the statistical analysis plan.

Details of analysis for the Extension part will be defined in a SAP document.

[figure not shown]

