2. The Cut-off 2 analysis will be conducted when the last patient completes all assessments up to the Week 48 visit. The analysis will also include assessments of maintenance of efficacy and extended safety during the extension part and data from the Safety FU period for patients who prematurely discontinued from study treatment before the cut-off 2. Any between treatment comparison will be based on treatment assignment in the core part. The analysis will also be used in support of the registration of ofatumumab in Japan.
3. The final analysis will be conducted when the last patient completes the EOS visit or Safety FU period.

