2.1.1 General definitions

Study drug/treatment refers to the investigational drug Ofatumumab and placebo.

“Date of Cut-off 2” is expected as the date the last patient completes all assessments at Week 48 visit. If the last patient discontinues from the study prior to Week 48 visit, “date of Cut-off 2” is the last patient's last visit.

Date of first administration of study drug/treatment, or first date of study drug/treatment, is defined depending on the analysis purposes.

- For Cut-off 1 analysis and Cut-off 2 and final *efficacy* analysis, it refers to the date when the first dose of randomized treatment is administered.
- For Cut-off 2 and final *safety* analysis, it refers to the date when the first dose of ofatumumab is administered.

Date of last administration of study drug/treatment, or last date of study drug/treatment is defined by analysis time point.

- For Cut-off 1 analysis, it refers to the date when the last dose of randomized treatment is administered up to Week 24 visit.
- For Cut-off 2 analysis, it refers to the date when the last dose of treatment is administered up to the date of Cut-off 2.
- For final analysis, it refers to the date when the last dose of treatment is administered up to EOS visit.

Study day is defined as: if after first date of study drug, then (Study Day) = (Date) – (first date of study drug) +1; if before first date of study drug, then (Study Day) = (Date) – (first date of study drug); Study Day 1 is defined as the date of the first administration of study drug; there is no Study Day 0.

Duration of an event is calculated as (event end date) – (event start date) +1.

1 month is counted as 30 days unless otherwise specified.

Baseline is defined for each cut-off analysis.

- For Cut-off 1 analysis, and Cut-off 2 and final *efficacy* analysis, baseline is defined as the last non-missing result before or on the first date of study drug.
- For Cut-off 2 and final *safety* analysis, definition of baseline depends on each patient's treatment course in the study
 - For a patient continuously having ofatumumab across Core and Extension parts, baseline is defined as the last non-missing result before or on the first date of study drug.
 - For a patient switching the treatment from placebo to ofatumumab when entering the Extension part, baseline is defined as the dose date of ofatumumab at Week 24. *For analysis on vital signs*, the baseline is defined as *the pre-dose measurement* at Week 24.

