The adjusted ARR (i.e., model-based estimate adjusted for covariates) for each treatment and the corresponding 95% confidence interval, and ARR ratio (also expressed as percentage reduction relative to control group) along with the 95% confidence interval for the ARR ratio and the corresponding p-value will be obtained.

The definition of a confirmed MS relapse is one accompanied by a clinically relevant change in the EDSS assessment, i.e. an increase of at least 0.5 points on the EDSS (total) score, or an increase of at least 1 point on at least two Functional scores (FSs), or an increase of at least 2 point on at least one FS, excluding changes involving bowel/bladder or cerebral FS, compared to the last EDSS assessment taken in the absence of (confirmed or unconfirmed) relapse and prior to the current relapse. EDSS obtained on the date as indicated on the Summary of MS

Relapse eCRF page will be used. If such EDSS assessment is missing or not meeting the criteria to confirm the relapse, all other EDSS assessment taken within 30 days from the relapse start date (i.e., EDSS assessment date – relapse start date ≤ 30) and before the relapse end date (EDSS assessment date \leq relapse end date) will be checked. If at least one of such available EDSS assessments meets the criteria, the relapse is a confirmed one. Otherwise, the relapse is considered an unconfirmed one.

The patient's time in study for ARR at each cutoff will be calculated as (Cutoff point – first dose date + 1)/365.25.

The analysis will be performed at Cut-off 1 analysis. The adjusted ARR for each treatment and the corresponding 95% confidence interval will be provided also for Cut-off 2 analysis ([Section 2.14](#)).

Time to first confirmed relapse

Time to first confirmed relapse will be calculated as (start date of first confirmed relapse – date of first administration of study drug + 1). For patients without confirmed relapses at a cutoff point, they are censored with censoring time as time in study at the corresponding cutoff point.

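### The SAP leaves open whether Cut-off 2 efficacy uses the FAS or the Extension FAS; if the latter, results counted from Day 1 omit everyone who stopped in the Core part

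*SAP*

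**What the plan says.** - **Membership.** SAP 2.2: "The EFAS will include all FAS subjects who received at least one dose of ofatumumab during Extension part". SAP 2.1.4 builds the Cut-off 2 and final groups the same way; the delayed group is "patients randomized to placebo treatment group, and having at least one dose of ofatumumab in Extension part", with a parallel condition for the ofatumumab arm.
- **Data used.** SAP 2.2: "Analyses on EFAS will include *all* available efficacy assessments of the Core and Extension parts".
- **Time origin.** For first study-drug date in Cut-off 2 and final efficacy, SAP 2.1.1 says "it refers to the date when the first dose of randomized treatment is administered". In SAP 2.7.2 the patient's "time in study for ARR at each cutoff will be calculated as" the span from first dose to the cut-off point.
- **Who can qualify.** Under Protocol 3.1.1 and 3.1.2, only patients who complete the double-blind period enter the Extension. Core stoppers go to the EOS visit and Safety FU.
- **Commitment.** Protocol 9.7: "The main between-group comparisons of the efficacy variables will be based on the original randomization at the start of the Core part". SAP 1.1, on Cut-off 2: "Any between treatment comparison will be based on treatment assignment in the core part". The protocol summary applies intention-to-treat to all efficacy data.
- **Competing text.** SAP 2.2 assigns all efficacy analyses to the FAS. SAP 2.7 makes the FAS the default unless another set is named. The T2, ARR and time-to-relapse paragraphs of SAP 2.7.2 name the FAS and then extend to Cut-off 2.
- **Declared changes.** SAP Section 4 lists five departures from the protocol. The Extension-dose condition is not among them.

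**The concern.** The Extension FAS applies a membership rule decided at Week 24 to events counted from Day 1. Arm labels follow randomization, but the population no longer does, because a patient who stopped in the Core part cannot be a member. Stopping could be linked to the outcome: Protocol 3.4 has relapsing patients informed again about other treatments and adds that "Patients can select to discontinue study treatment and consider to start treatment with an approved MS therapy". The planned relapse rate is 2.5 times as high on placebo (0.40 against 0.16), so any such link need not act equally in the two arms.

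The exposed results are the adjusted ARR by arm with its interval, the Kaplan-Meier relapse estimates, and the Gd and T2 lesion analyses repeated at Cut-off 2. SAP 1.1 says the Cut-off 2 analysis also supports registration in Japan.

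**Working it through.** **1. Which set governs?** For the Extension FAS: the SAP document history says it was defined for efficacy including the Extension; SAP 2.3 puts Cut-off 2 disposition and baseline on it; SAP 2.15 takes time up to Week 24 from the Week 24 visit date, with no rule for an earlier stopper. For the FAS: the competing text above, and the fact that SAP 2.7.2 and 2.15 never name the Extension FAS. SAP 2.14, to which the Cut-off 2 analyses refer, is not visible in the public copy. The visible text supports both sets.

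**2. Plan's own figures.** Inputs from Protocol 9.9 and 9.9.2: 60 patients at 2:1 (40/20), 10% dropout, ARR 0.40 and 0.16, dispersion 0.1, 6 months. Expected relapses are 20 × 0.20 = 4.0 on placebo and 40 × 0.08 = 3.2 on ofatumumab. Exact enumeration of the negative binomial arm totals gives P(ARR ratio < 1) = 83.6%, or 81.8% with 36/18. Both agree with the stated figure of more than 80%.

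**3. Patients lost.** If the 10% allowance is all Core stopping (assumption): 2 of 20 placebo and 4 of 40 ofatumumab, leaving 54.

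**4. Effect on Core-period rates.** Let a share d of an arm stop, with m times the completers' event rate x. Then overall rate = (1 − d)x + dmx, so the rate in the Extension FAS is

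x = overall rate / (1 − d + dm).

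With d = 0.10 the divisor is 1.0, 1.1 or 1.3 for m = 1, 2 or 4. The values of m are assumptions.

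| Whose stoppers are more active | Placebo ARR | Ofatumumab ARR | ARR ratio (true 0.40) | Gd ratio (true 0.080) |
|---|---|---|---|---|
| Neither (m = 1) | 0.400 | 0.160 | 0.40 | 0.080 |
| Placebo only, m = 2 | 0.364 | 0.160 | 0.44 | 0.088 |
| Placebo only, m = 4 | 0.308 | 0.160 | 0.52 | 0.104 |
| Ofatumumab only, m = 2 | 0.400 | 0.145 | 0.36 | 0.073 |
| Ofatumumab only, m = 4 | 0.400 | 0.123 | 0.31 | 0.062 |
| Both, m = 2 or 4 | 0.364 or 0.308 | 0.145 or 0.123 | 0.40 | 0.080 |

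With no true effect, the same one-arm cases give ratios from 1/1.3 = 0.77 to 1.30. If m is the same in both arms (2 or 4) but stopping is 15% in one and 5% in the other, the ARR ratio runs from 0.32 to 0.50.

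**5. If relapse itself triggers stopping.** Over 168 days, mean relapses are 0.40 × 168/365.25 = 0.184 and 0.16 × 168/365.25 = 0.0736. The chance of at least one is 1 − 1.0184^(−10) = 16.7% on placebo and 1 − 1.00736^(−10) = 7.1% on ofatumumab. If a fraction f of relapsers stop, the retained ARR is ARR × (1 − f)/(1 − f × P). With f equal in both arms at 25%, 50% or 75% (assumption), the ratio is 0.39, 0.38 or 0.37. With f = 50% on placebo only, placebo ARR is 0.40 × 0.5/(1 − 0.5 × 0.167) = 0.218 and the ratio 0.16/0.218 = 0.73.

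**6. Placebo-arm ARR over 48 weeks.** Assume completers' rate falls to 0.4x after the switch and stoppers stay at mx and remain observed. The Extension FAS gives 0.7x; the FAS gives 0.9 × 0.7x + 0.1mx. For m = 1, 2, 4: 0.280, 0.255, 0.215 against 0.292, 0.302, 0.317.

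**The case against.** Several points against the concern stand.

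- Protocol 9.7 goes on to describe the placebo comparator as patients who received delayed ofatumumab at the start of the Extension, and leaves details to the SAP. The protocol summary gives the Week 48 purpose as data on continuous ofatumumab treatment. So a reader might infer that the SAP plainly breaks a protocol promise, but 9.7 can itself be read as conditioning the placebo arm on Extension entry. It does not say this of the ofatumumab arm, and it sits beside the intention-to-treat statement.
- The FAS wording may be what the sponsor intends. The defect that can be shown is a contradiction, not a proven exclusion.
- At Cut-off 2 the Cox model is not run, ARR is given by arm, and SAP 2.15 is descriptive. An ARR ratio is not a specified Cut-off 2 output; it serves here to show relative distortion. Whether the repeated lesion analyses include a rate ratio and p-value is itself unclear.
- Relapse-driven exclusion is an inference. Protocol 3.4 also lets relapsing patients stay and offers placebo completers ofatumumab, and many stopping reasons in Protocol 5.6.2 have nothing to do with relapse.

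None of this settles which set applies or puts the condition into SAP Section 4.

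**Conclusion.** The point holds as a contradiction with a conditional consequence. If the Extension FAS is used, Cut-off 2 efficacy counted from Day 1 is restricted to Core completers and is not all-randomized, without being declared.

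The size rests on assumptions. At 10% stopping in each arm, with only one arm's stoppers having 2 to 4 times the event rate, a true ARR ratio of 0.40 appears as 0.31 to 0.52. There is no bias if stopping is unrelated to disease activity, and little if stopping is equally related and about equally frequent in both arms.

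A reader might infer that placebo rates are certainly biased low, or that the ratio moves from 0.40 to 0.73. The documents do not support either. They give no data on who stops, and 0.73 needs half of placebo relapsers to stop and no ofatumumab relapsers. That case would work against the drug, and the opposite direction is equally possible. The primary endpoint, regional consistency and all other Cut-off 1 analyses stay on the FAS and are unaffected.

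**What to change.** 1. State in SAP 2.2 and 2.7.2 that Cut-off 2 efficacy analyses counted from Day 1 use the FAS by randomized arm. Core stoppers contribute their available data and follow-up time; relapses are still collected in Safety FU (Protocol Table 6-2). Define the ARR follow-up end for these patients.
2. Keep the Extension FAS for post-Week-24 summaries and for the SAP 2.15 switch summaries, labelled as Extension entrants only. Show the FAS result up to Week 24 alongside. Do not use the FAS before Week 24 and the Extension FAS after it within one switch summary: the before and after periods need the same patients, or the change of population is mixed with the switch effect.
3. Reconcile SAP 2.2, 2.7 and 2.7.2, and name the set for each Cut-off 2 efficacy output.
4. List any remaining departure from Protocol 9.7 in SAP Section 4.

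The cost is SAP wording and a population switch in a few tables, rerun if they already exist. No new data are needed.

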3.1.2 Extension part

The Extension part consists of 2 periods; **Double-blind loading dose period** and **Open-label treatment period**.

The **Double-blind loading dose period** will be applicable for patients who complete the Double-blind treatment period. All patients will receive ofatumumab 20 mg sc at Week 24; the Extension part starts with the injection of the Week 24. Patients randomized to ofatumumab in the Double-blind treatment period will receive the matching placebo sc at Week 25 and 26. Patients randomized to placebo in the Double-blind treatment period will receive ofatumumab 20 mg sc at Week 25 and 26. All patients will receive the study drug in a double-blind manner at Week 25 and 26.

The **Open-label treatment period** will begin at Week 28 and all patients will receive open-label ofatumumab 20 mg sc every 4 weeks in this period. This period will continue until the last patient is transferred to a planned umbrella extension study (under separate protocol requiring another informed consent).

Patients who prematurely discontinue study treatment will have their EOS visits as soon as possible and will be followed up for safety in the Safety FU period ([Section 3.1.3](#)) for a minimum of 36 weeks ([Table 6-2](#)). After study drug discontinuation, during Core or Extension parts, patients may initiate alternative MS therapy according to local standard of care if clinically indicated (see [Section 5.6.2](#)).

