2.8 Safety analyses

Safety analyses during the study will be detailed below. All safety analyses will be based on the SAF for Cut-off 1 analysis and ESAF for Cut-off 2 and final analysis, unless explicitly stated otherwise.

Patients will be grouped by the actual treatment received. Safety data for the core part will be reported for the first time when the double-blind loading dose period has been completed by the last patient (Cut-off 1 analysis). Safety data for the extension part including Safety FU period

data will be reported for the first time when the last patient has finished 48 weeks of treatment (Cut-off 2 analysis). Safety data beyond the cut-off 2 will be reported separately.

Unless explicitly otherwise stated, for patients who entered Safety FU period, safety data will be reported up to and including the safety cut-off.

- For Cut-off 1 analysis, safety data reported up to safety cut-off, the latest visit date including Safety FU, or Week 24 visit date, whichever comes first.
- For Cut-off 2 and final analysis, safety data reported up to safety cut-off or the latest visit date including Safety FU, whichever comes first.

The assessment of safety will be primarily based on the frequency of adverse events (including death and non-fatal serious adverse events). Additional safety assessments include laboratory tests, physical examination (including examination of skin), vital sign measures, ECG evaluations and assessment of suicidality. Clinically significant findings in these additional safety assessments will be reported as adverse events and analyzed as such. In addition, all safety assessments will be summarized or listed as appropriate.

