2.8.1 Adverse events (AEs)

Treatment emergent adverse events (TEAE) is defined as any adverse event which start on or after the day of the first dose of study drug.

TEAEs will be reported if their onset days are no greater than “time at risk for AE”. Similarly, serious TEAEs will be reported if their onset days are no greater than “time at risk for SAE”.

TEAE will be coded by primary system organ class and preferred term according to the Medical Dictionary for Regulatory Activities (MedDRA). The MedDRA version used for reporting the study will be described in a footnote.

Incidence of TEAEs will be summarized (number and percentage of patients reporting any TEAE by primary SOC, preferred term, and treatment group. Serious TEAEs, drug related TEAEs, TEAEs leading to premature discontinuation from study drug, TEAE leading to study drug interruption, and most common TEAEs ($\geq 5\%$ in any of the treatment groups) will be presented in a similar format as adverse events. In addition, incidence of TEAEs will be summarized by SOC, preferred term, and maximum CTCAE grade. Missing CTCAE grade will not be imputed. The CTCAE version 5.0 will be used.

For Cut-off 1 analysis, odds ratios (investigational drug vs. control) with 95% confidence intervals will be presented along with the summary of any TEAEs and the summary of serious TEAEs. Details in calculations of odds ratios and their 95% confidence intervals are provided in Section 5.7.1. Incidence of any TEAEs will be plotted by SOC, along with the odds ratio (and corresponding 95% confidence interval) for TEAEs in each SOC. Odds ratios provide appropriate inferences for events that are likely to occur at certain times (e.g., injection related reactions) while no constant risk over time is expected.

If a patient reports more than one adverse event within the same primary SOC, the patient will be counted only once with the maximum CTCAE grade at the SOC level, where applicable.

All AEs will be presented in listings.

The following summaries will be repeated for Cut-off 2 and final analysis:

- Overall TEAE
- TEAE by CTCAE grade
- Serious TEAE
- Drug-related TEAE
- TEAE causing study drug discontinuation
- TEAE leading to study drug interruption
- Serious TEAE causing study drug discontinuation
- Most common TEAE
- Infections and infestations TEAE

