2.8.1.2 Adverse events by onset period

Incidence of TEAE will be displayed by first onset period. The following periods will be displayed:

- Day 1 – Month 3 (Day 1 – Day 90)
- Month 3 – Month 6 (Day 91 – Day 180)
- Month 6 – Month 9 (Day 181 – Day 270)
- Month 9 – Month 12 (Day 271 – Day 360)
- Month 12 or later (Day 361 or later).

For each period, incidence of an AE will be the proportion of patients with the AE among patients “at risk”. As seen section 2.4.1, “time at risk” will be defined in two ways for overall AE and SAE. Then two types of summary will be provided:

- Incidence of overall AE by first onset period: This will be based on time at risk for AE. Then *no SAE will be counted if it is reported after safety cut-off* in this analysis.
- Incidence of SAE by first onset period: This will be based on time at risk for SAE.

This analysis will be performed only for Cut-off 2 analysis.

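### At Cut-off 2 and the final analysis, the OMB 20mg safety column counts from Core Day 1 but admits only patients dosed in the Extension, so no permanent Core-part stop can appear in it

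*SAP*

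**What the plan says.** SAP 2.2 defines the set: "The ESAF set includes all subjects who received at least one dose of ofatumumab during Extension part". It limits the data to assessments "only under ofatumumab treatment during the Core and Extension parts". SAP 2.8 makes this the default population, using SAF for Cut-off 1 and "ESAF for Cut-off 2 and final analysis, unless explicitly stated otherwise". SAP 2.1.4 defines the OMB 20mg safety column the same way: "This will include patients treated with ofatumumab during Core part and having at least one dose of ofatumumab in Extension part".

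Protocol 3.1.2 settles who can receive that dose. The loading-dose period that opens the Extension "will be applicable for patients who complete the Double-blind treatment period". Under Protocol 3.1.1, a patient who stops double-blind drug early goes to the EOS visit and then to Safety Follow-up.

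SAP 2.1.1 sets the clock. For Cut-off 2 and final safety analyses, the first date of study drug is defined so that "it refers to the date when the first dose of ofatumumab is administered". Table 2-11 in SAP 2.4.1 starts time at risk for both AEs and SAEs from that date.

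The summaries that SAP 2.8.1 repeats at Cut-off 2 and final include overall, serious and drug-related TEAEs and "TEAE causing study drug discontinuation". In SAP 2.8.1.2 (Cut-off 2 only), for each onset period "incidence of an AE will be the proportion of patients with the AE among patients" at risk.

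**The concern.** Membership of the OMB 20mg column is decided at Week 24, but its events and risk time are counted from Core Day 1. This is guaranteed (immortal) time: every patient in the column is known in advance to have stayed on treatment through Core. Ofatumumab patients who permanently stopped in Core lose both their events and their exposure, while the continuers' Core exposure is counted in full.

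The Placebo – OMB column differs. Its clock starts at its qualifying Week 24 dose, so stops in its first 24 weeks on ofatumumab are counted. Side by side, the two columns do not describe the same thing over the first 24 weeks of ofatumumab.

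SAP 1.1 says the Cut-off 2 analysis supports registration in Japan. A reader would take the column as the safety experience on ofatumumab from the first dose, whereas it describes only those who stayed on treatment for 24 weeks.

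**Working it through.** The documents give no figure for ESAF, so there is nothing to reproduce. The check traces the definitions and then sizes the effect from the planned numbers.

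**Inputs.** 60 patients randomized 2:1, so 60 × 2/3 = 40 on ofatumumab, with a 10% dropout allowance (SAP 3). The Core part is 24 weeks = 168 days (SAP 1.1). Minimum safety follow-up is 36 weeks = 252 days (Protocol 3.1.3). The 5% and 20% dropout rates, the split of stops by cause, and equal dropout in both arms with all of it in Core are assumptions.

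**Step 1: a patient who stops ofatumumab for good in Core.**
- ESAF and OMB 20mg column (SAP 2.2, 2.1.4): no Extension dose, so not a member.
- Cut-off 1 (SAP 2.2): included, on SAF. SAE time at risk ends at the end date of the Core part (Table 2-10), the day all randomized patients have completed Week 24 or stopped drug before it.
- Safety Follow-up summaries (SAP 2.8.4.4): no set is named. The default in SAP 2.8 would be ESAF, but the reference there to everyone who entered follow-up suggests a wider set.

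The exclusion depends on the date of the stop. An event that begins in Core and leads to a stop in the Extension still appears.

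**Step 2: patients left out, and Core time in which no permanent stop can fall.** Patients left out = 40 × dropout. Core time = patients kept × 168 / 365.25.

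| Dropout | Left out | Kept | Core patient-years |
|---|---|---|---|
| 5% | 2 | 38 | 17.5 |
| 10% | 4 | 36 | 16.6 |
| 20% | 8 | 32 | 14.7 |

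That Core time is 24/48 = 50% of treatment time for a patient followed 48 weeks, and 24/72 = 33% at 72 weeks. In the onset-period table it covers all of Day 1–90 and Day 91–180 up to about Day 168.

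**Step 3: discontinuation for an adverse event.** Assume 1 such stop in the Extension and 4 Core stops of any cause, of which c are for adverse events. All exposed: (1 + c)/40. ESAF: 1/36.

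| c | All exposed | ESAF |
|---|---|---|
| 0 | 1/40 = 2.5% | 2.8% |
| 1 | 2/40 = 5.0% | 2.8% |
| 2 | 3/40 = 7.5% | 2.8% |
| 4 | 5/40 = 12.5% | 2.8% |

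The ESAF figure does not respond to c.

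**Step 4: SAE follow-up outside both sets of TEAE tables.** A Core stopper with the minimum follow-up who stopped d days before the end date of the Core part has about max(0, 252 − d) days that Cut-off 1 does not cover and ESAF excludes: 252, 152, 84 and 0 days for d = 0, 100, 168 and 252.

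**The case against.** The strongest reply is that ESAF matches the protocol's target. The protocol summary (Data analysis) speaks of the 48-week continuously treated group for the Japanese submission, and Protocol 9.7 repeats the idea of continuous treatment and defers details to the SAP. That justifies a continuing-patient summary. It does not say that exposed patients who stopped should be left out, and Protocol 9.1 uses the Safety Set for all safety analyses.

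Second, Core stoppers are reported elsewhere. SAP 1.1 puts their follow-up data into Cut-off 1, which also supports registration. SAP 2.3 bases final disposition on FAS, SAP 2.8.1 and 2.8.2 list all AEs and deaths, and SAP 2.8.4.4 promises a complete follow-up analysis in an addendum. This stands as a limit: the data are not lost. It does not put these patients back into the combined tables, and the Cut-off 1 tables stop at the end date of the Core part.

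Third, SAP 1.1 and SAP 4 item 1 say Cut-off 2 includes Safety Follow-up data from early stoppers. That could be met by separate follow-up outputs or by Extension stoppers alone. Their plain wording covers Core stoppers too, so the text still needs reconciling.

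Fourth, the bias need not run downward in every table. If Core stoppers left for other reasons and had few events, removing them can raise a percentage, as the c = 0 row shows. This is correct: a low figure is a firm expectation only for the discontinuation table, and only if someone stopped in Core for an adverse event.

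Fifth, the size may be modest. In the subcutaneous Phase 2 study (Protocol 1.1), 214 of 231 completed 24 weeks. That leaves 17/231 = 7.4% stopping, all arms and causes pooled, or about 40 × 0.074 = 3 patients. This is inside the range shown.

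Some outputs do not use ESAF: compliance (SAF), suicidality (Safety Set), and the B-cell, PK and ADA summaries of SAP 2.10 and 2.11 (FAS). Protocol 15.1 and 15.4 mention restarting drug after discontinuation without saying whether such a patient could enter the Extension. The point therefore concerns permanent stops. No between-column test is planned at Cut-off 2.

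**Conclusion.** The concern holds. As written, the Cut-off 2 and final discontinuation table cannot be right for ofatumumab exposure from the first dose, because permanent Core stops are excluded by definition. For the overall, serious and drug-related TEAE tables and the onset-period table, proportions can be too low, but the direction is not guaranteed.

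The size rests on the number of Core stops on ofatumumab, which the documents do not give. It is nil if there were none. About 4 of 40 would be missing under the planned allowance, and 2 to 8 under the assumed range. The ESAF tables alone cannot show how much is missing. A secondary gap is that a late SAE in a Core stopper's follow-up can fall outside both the Cut-off 1 and the ESAF TEAE tables, leaving it to listings and to a follow-up summary whose population is not named.

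The SAP's document history records the extension safety set under Amendment 2 (20-Jul-2020), but SAP 4 does not list it among the changes to protocol-specified analyses.

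**What to change.** For the Cut-off 2 and final ofatumumab safety summaries (at least the TEAE, serious TEAE, discontinuation and, at Cut-off 2, onset-period tables), use a set of all patients with at least one ofatumumab dose in either part, counted from the first ofatumumab dose. Keep ESAF as the supportive continuous-treatment set that answers the protocol summary's wording.

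In SAP 2.8.4.4, name the set for the Safety Follow-up summaries so that Core stoppers are included. Align SAP 2.1.4, 2.2 and 2.8 with the Cut-off 2 description in SAP 1.1, and enter the safety-set change in SAP 4.

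The cost is one population flag and these wording changes. A few more patients may enter the tables, and the reported adverse event and discontinuation rates may be slightly higher.
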